## REVISION HISTORY

No need to review this section if this is the first version of the protocol you are submitting to the IRB

Revision #	Version Date	Summary of Changes
1	20APR22	New protocol template.
2	20APR22	Statement to include Ketorolac is not indicated for use in the pediatric population. (Section 5)

## 1. Study Summary

Project Title	Ketorolac as a Strategy for Reducing Post-Operative Opioid Requirement in Children with OSA undergoing Adenotonsillectomy: A Randomized Controlled Trial
Project Design	This study is designed as a randomized controlled trial with participants assigned to either Ketorolac or Morphine.
Primary Objective	Determine the effect of Ketorolac administration on total postoperative Morphine dosage required to achieve analgesia in children
Secondary Objective(s)	Characterize the effect of intra-operative ketorolac administration on FLACC pain scores and PACU recovery time
Research Intervention(s)/Interactions	Ketorolac or Morphine for post-operative
Study Population	Children's Healthcare of Atlanta- Egleston
Sample Size	120
Study Duration for individual participants	One Day
Study Specific Abbreviations/ Definitions	OSA: Obstructive Sleep Apnea
Funding Source (if any)	Department: Atlanta Gas Light funds

## 2. Objectives

Our primary aim is to determine the effect of ketorolac administration on total postoperative morphine dosage required to achieve analgesia in children with OSA undergoing adenotonsillectomy. Our secondary aim will be to characterize the effect of intra-operative ketorolac administration on FLACC pain scores and PACU recovery time. The measures we will monitoring are PACU morphine requirements, FLACC pain scores, PACU recovery time, incidence of post-tonsillectomy bleeding and total amount of pain medications administered during hospitalization.

## 3. Background

Obstructive sleep apnea (OSA) as an indication for adenotonsillectomy has increased significantly over the past ten years, and now has surpassed recurrent tonsillitis as the most

common indication for this procedure. Opioids continue to be the most commonly administered pain medication for these procedures. Studies have shown that patients with OSA have significantly increased sensitivity to opioids that results in post-operative respiratory

depression and apnea when administered via standard opioid dosing protocols. Children with OSA were shown to have a nearly fivefold increase in the odds of developing respiratory complications when compared to their counterparts with tonsillitis. As such, it is imperative that current anesthetic management of children undergoing this procedure remains as safe and effective as possible for this growing population. Ketorolac possesses similar efficacy to morphine without the same incidence of respiratory depression, nausea and vomiting, which are commonly seen post-adenotonsillectomy. Importantly, when combined with opioids, ketorolac is opioid-sparing. This synergistic effect means that a similar level of analgesia is achieved using a lower dose of opioid. However, there continues to be concern about using ketorolac due to the potential risk of post-operative bleeding from anti-platelet activity.

To our knowledge, the use of ketorolac as part of an analgesic regimen has not yet been studied in the specific population of children with OSA undergoing adenotonsillectomy, though they stand to benefit from it the most. In this randomized prospective study, we will determine the effect of ketorolac on the total dose of morphine required to achieve postoperative analgesia in children with OSA undergoing adenotonsillectomy.

#### **4. Study Endpoints**

We hypothesize that by administering ketorolac at the end of the procedure once hemostasis has been achieved, we can decrease the amount of morphine administered in the PACU. By decreasing FLACC pain scores and opioid administration, we aim to decrease the PACU length of stay. Additional costs are incurred due to utilization of additional resources, increased length of stay, and unanticipated intensive care. This study will provide a more comprehensive understanding of the efficacy and safety of the current standard postoperative analgesic regimen employed at our institution, in which opioid analgesia currently plays a prominent role.

#### **5. Study Intervention/Investigational Agent**

Although not indicated for use in the pediatric population, Ketorolac possesses similar efficacy to morphine and other major opioid analgesics, but does not cause respiratory depression and is not associated with nausea and vomiting, both commonly described complications post-adenotonsillectomy. Importantly, when combined with opioids, it is opioid-sparing. This synergistic effect means that a similar level of analgesia is achieved using a lower dose of opioid. Improved quality of analgesia, in addition to reduction of opioid-related adverse effects, makes ketorolac an ideal adjuvant to study in an OSA population. While data remain mixed as to whether ketorolac contributes to increased hemorrhage post-adenotonsillectomy through

inhibition of platelet aggregation and prolonged bleeding time, several studies have recently emerged that are either reassuring or equivocal.

A systematic review and meta-analysis showed that while ketorolac is associated with a five-fold bleeding risk in adults after any surgical procedure, children under 18 were not at a significantly increased risk for bleeding post-tonsillectomy. Another quantitative systematic

review showed that while NSAIDs were equianalgesic when compared with opioids, and the risk of emesis was significantly decreased, the evidence for NSAIDs to increase bleeding risk post-tonsillectomy was equivocal. A recently updated Cochrane study reviewed 15 trials assessing the effect of NSAIDs on bleeding in children undergoing elective tonsillectomy or adenotonsillectomy, which found no significant increased risk of bleeding when NSAIDs are used in pediatric tonsillectomy.

## **6. Procedures Involved**

After consent has been obtained, patients will be randomly assigned to ketorolac group or non-ketorolac group. All patients will receive a similar anesthetic with inhalational induction with the exception of the ketorolac group receiving 0.5mg/kg IV ketorolac at the end of the procedure once hemostasis has been achieved. The PACU nurses, who will be blinded to ketorolac administration, will evaluate the patients using FLACC scores at 10 minutes post-op, 20 minutes post-op and at time of PACU discharge. For patients with a FLACC score of 6-10, morphine 0.05mg/kg will be administered. For patients with FLACC scores of 3-5, morphine 0.025mg/kg will be administered. The total amount of opioid required to obtain a FLACC score of less than 3 will be evaluated as the primary outcome. The secondary outcomes to be evaluated will be PACU FLACC scores, time required in PACU, incidence of post-tonsillectomy bleeding and total pain medications administered during hospital admission.

All patients will undergo inhalational induction with Nitrous Oxide and Sevoflurane. After IV placement, propofol 1-3mg/kg and fentanyl 1mcg/kg will be administered prior to intubation. Immediately after induction, dexamethasone 0.5mg/kg and an IV infusion of acetaminophen 15mg/kg will be administered. During the intra-op course, dexmedetomidine 0.5mcg/kg and odansetron 0.1mg/kg will be given. Patients in the ketorolac group will receive 0.5mg/kg IV, while those in the non-ketorolac group will not receive any.

A rescue dose of Fentanyl 0.5-1mcg/kg IV will be available for administration at the end of the procedure. The decision to administer this will be left to the discretion of the attending anesthesiologist for the case. The choice to give this will be made based on variables including patient's condition and a 20% increase in the heart rate and blood pressure. In PACU, nurses will be blinded to ketorolac administration, but will be informed of all other medications given.

---

**Protocol Title:** Ketorolac as a Strategy for Reducing Post-Operative Opioid Requirement in Children with OSA undergoing Adenotonsillectomy: A Randomized Controlled Trial

---

The PACU nurses will evaluate the patients using FLACC scores at 10 minutes post-op, 20 minutes post-op and at time of PACU discharge. For patients with a FLACC score of 6-10, morphine 0.05mg/kg will be administered. For patients with FLACC scores of 3-5, morphine 0.025mg/kg will be administered. For patients with FLACC scores of 0-2, no morphine will be administered. The total amount of morphine required to obtain a FLACC score of less than 3 will be recorded.

The PACU length of stay will be monitored as a secondary outcome, as decreasing the PACU length of stay may also be a benefit of ketorolac administration. In addition, we will monitor for post-tonsillectomy bleeding and categorize as either post-tonsillectomy bleeding requiring surgical intervention or post-tonsillectomy bleeding not requiring surgical intervention. In addition, the total amount of pain medication required during hospitalization will be evaluated. Once the patient is discharged, there will be no further collection of data or follow-up with the participant.

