## **22. Informed Consent**

Only those patients who meet the Inclusion criteria will be considered as possible study candidates. A thorough discussion between the parents or legal guardian and the principal investigator, or the study coordinator will occur during the study consent process. No study related procedure will occur prior to obtaining appropriate informed consent. Patients will be enrolled consecutively as they present to Children's Healthcare of Atlanta. The parents or legal guardian of the patient will be approached in clinic prior to surgery by the principal investigator, or the study coordinator to discuss the goals, benefits and risks of the project. Written informed consent will be obtained following this discussion. For the occasions when parents do not arrive at the hospital until the day of surgery, they will be approached only if there is sufficient time to allow for their full consideration. One parent even if the other parent is alive, known, competent, reasonably available, and shares legal responsibility for the care and custody of the child.

Patients undergoing emergent/urgent procedures or when there is insufficient time for the parents to thoroughly consider the goals, benefits and risks of this project will not be approached for enrollment.

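### Assignment follows consent but treatment comes only at the end of surgery, and only PACU nurses are blinded, so surgeon and anesthesiologist can know the arm during the operation

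*Combined protocol and SAP*

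**What the plan says.** All of this comes from the combined protocol and SAP.

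- **Assignment.** Section 6: "After consent has been obtained, patients will be randomly assigned to ketorolac group or non-ketorolac group". No time is given relative to induction, surgery or hemostasis.
- **Consent.** Section 22: "The parents or legal guardian of the patient will be approached in clinic prior to surgery by the principal investigator, or the study coordinator". Families who first arrive on the day of surgery may be approached then, if there is time.
- **The difference between arms.** Section 6 describes a similar anesthetic for all, "with the exception of the ketorolac group receiving 0.5mg/kg IV ketorolac at the end of the procedure once hemostasis has been achieved". In the comparator, children get no ketorolac ("while those in the non-ketorolac group will not receive any"), and no placebo or sham injection is described.
- **Blinding.** Section 6: "In PACU, nurses will be blinded to ketorolac administration, but will be informed of all other medications given". Nothing is said about the surgeon or the anesthesiologist.
- **Dispensing.** Section 23 has the hospital pharmacy release the drug after randomization, for use in the operating room.
- **Discretion in the operating room.** Section 6 gives propofol as a range and leaves end-of-case rescue fentanyl to the attending anesthesiologist.
- **Withdrawal.** Section 14 allows a child to be withdrawn if no paralytic is given or if the surgery is scheduled after hours.
- **Analysis.** Section 7 compares baseline characteristics by receipt of ketorolac. It then models narcotic use in two cohorts that it does not define by assignment.

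**The concern.** The treatment difference begins at the end of the operation, so nothing requires the arm to be known earlier. If it is known earlier, people who are not blinded can act on it, and some of what they control feeds into the outcomes.

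- **Hemostasis.** Bleeding is a secondary outcome, split into "post-tonsillectomy bleeding requiring surgical intervention or post-tonsillectomy bleeding not requiring surgical intervention", and Section 3 names it as the worry about ketorolac. A surgeon who knows that ketorolac is coming may take more care over hemostasis in that arm. This could hide an increase caused by the drug.
- **Anesthetic and rescue fentanyl.** A different background anesthetic, or a different readiness to give fentanyl at the end, could change PACU pain, morphine need and length of stay for reasons other than ketorolac.
- **Withdrawals.** Whether a paralytic is given is decided in the operating room. If that happens after assignment, with the arm known, the two groups need no longer be comparable.

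The Section 7 adjustment for patient and surgical characteristics is not a dependable remedy, because the plan does not list hemostatic effort among the data to be recorded.

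**Working it through.** **Order of events.** Putting Sections 6, 14, 22 and 23 in sequence gives:

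1. Consent, in clinic or on the day of surgery (Section 22).
2. Assignment, after consent (Section 6).
3. Dispensing, after assignment (Section 23).
4. Induction and the rest of the anesthetic, including whether a paralytic is given (Sections 6 and 14).
5. Surgery and hemostasis.
6. Ketorolac or nothing (Section 6).
7. Rescue fentanyl, if the anesthesiologist chooses, also at the end (Section 6).
8. PACU scoring and morphine by blinded nurses (Section 6).

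Only the order of steps 1, 2, 3 and 6 is fixed by the text. Placing step 2 ahead of steps 4 and 5 is the natural reading, but it is not written. Because the control arm receives nothing, a dispensed dose also reveals the arm to anyone who sees it.

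**Size.** Bias from knowledge of the arm cannot be computed, because no document gives a figure for changed behavior. The sample size of 120 (Section 12) cannot be reproduced either: no alpha, power, effect size, SD or allocation ratio is stated.

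**Illustration: ketorolac-arm children who go untreated.** Assume 60 per arm, two-sided alpha 0.05, a normal approximation, and a share f of the ketorolac arm not receiving the drug. The documents give no f, and f = 0 also fits the text.

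The difference detectable with 80% power is d = (1.960 + 0.842) × √(2/60) = 0.51 SD. Analyzed by assignment, the effect becomes (1 − f)d, and power = Φ[(1 − f) × 2.802 − 1.960]. The total needed to restore 80% is 2 × 60/(1 − f)², with each arm rounded up.

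| f | children | power | total to restore 80% |
|---|---|---|---|
| 0 | 0 | 80.0% | 120 |
| 2% | 1.2 | 78.4% | 126 |
| 5% | 3 | 75.9% | 134 |
| 10% | 6 | 71.3% | 150 |

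**Illustration: grouping by receipt.** Suppose the drug has no effect, both arms contain the same share f of such children, and their outcome is b SD worse. Moving the untreated ones into the comparator gives a false benefit of 2fb/(1 + f). With f = 5% this is 0.05/1.05 = 0.05 SD at b = 0.5 and 0.10/1.05 = 0.10 SD at b = 1. So the direction of the error depends on an analysis rule that Section 7 does not state.

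**Bleeding counts.** Section 15 quotes 3% after tonsil removal and 2% in children with OSA. With 60 per arm that is 60 × 0.02 = 1.2 to 60 × 0.03 = 1.8 expected bleeds, so one event is 56% to 83% of an arm's count. This shows how fragile the comparison is. It does not measure bias, and Section 15 gives no time window while data collection stops at discharge.

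**The case against.** The strongest reply is that the text fixes assignment only as following consent. Assignment during the operation would comply. That is correct: a reader might infer that assignment certainly precedes surgery, but the documents do not say so. What remains is that nothing prevents it, and Sections 6, 22 and 23 taken together point that way.

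A second tempting inference is that the hemostasis condition takes ketorolac away from some children in one arm only. The documents do not support this. The wording "the ketorolac group receiving 0.5mg/kg IV ketorolac at the end of the procedure once hemostasis has been achieved" reads as a statement of timing. No section says that the drug is withheld, or that any child ends surgery without hemostasis, and known coagulation defects are excluded in Section 10. Dilution is therefore a possibility with no stated frequency.

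Third, most background drugs in Section 6 are fixed per kilogram, the propofol range applies before intubation, and PACU morphine follows a fixed FLACC rule applied by blinded nurses. This narrows the path to the primary outcome but does not close it: rescue fentanyl is discretionary and comes just before PACU.

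Fourth, opening the allocation late does not by itself protect the rescue-fentanyl decision, since the anesthesiologist would still see ketorolac given or omitted. This stands, and the fix has to cover it. Concealing the dose from operating-room staff is a legitimate alternative route.

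**Conclusion.** The point holds as a design weakness that should be corrected. The plan lets the operation, the anesthetic and the no-paralytic withdrawal take place with the arm known to unblinded staff, although the arms do not differ until the end of the procedure. The affected comparisons are bleeding, PACU stay and, less directly, PACU morphine.

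The conclusion rests on the natural reading that assignment soon follows consent, and on the absence of any stated concealment in the operating room. The size of the bias is unknown. The power losses and bleed counts shown are illustrations under an assumed 60 per arm and assumed shares of untreated children, and should not be cited as estimates. If the hemostasis wording is purely about timing, the dilution argument falls away and the problem of knowledge of the arm remains.

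**What to change.** 1. **Section 6, timing.** Keep consent as planned. Keep the allocation sealed, or held by pharmacy, until hemostasis has been declared in the same way for every child and the study dose is due. Randomize at that point. Both Section 14 grounds, no paralytic and after-hours surgery, then become known before randomization.
2. **Section 6, rescue fentanyl.** Where feasible, have the decision made and recorded before the allocation is opened. Otherwise conceal the study dose from the anesthesiologist who decides. State who in the operating room is blinded.
3. **Section 23.** Align dispensing with the later randomization, for example by having a dose ready for release.
4. **Section 7.** Compare children by assigned group, and record hemostasis status in both arms.
5. **Children without hemostasis.** How they are managed is for the investigators to specify; the protocol should say it.

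The cost is protocol wording plus a pharmacy call or a sealed envelope at the end of surgery. Some prepared doses will be wasted (about half, if one is prepared for every child and allocation is 1:1), or a short pharmacy lead time is needed with the child under anesthesia. The target of 120 is unchanged if it is counted as randomized children. The conclusions would then apply to children who reach hemostasis, the point at which Section 6 has ketorolac given.

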## **15. Risk to Participants**

The drug that is being tested may not work any better than regular care. 1-10% of patients that take Ketorolac may have:

- Nausea
- Abdominal Pain
- Headaches

Serious, less common risks include:

- Post-procedure bleeding, after tonsil removal (3%), in children with OSA (2%)
- Less than (1%): chance of allergic or anaphylactic reaction.

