## **19. Provisions to Monitor the Data to Ensure the Safety of Participants**

Monitoring of Adverse Events (AEs) and Serious Adverse Events (SAEs) is an important aspect of data collection. After enrollment, the principal investigator or designee will collect the adverse experiences from the medical record. The study subjects will be reviewed on a case-by-case basis. The principal investigator will determine the seriousness of each adverse event and

whether or not the event was related to the study. Serious adverse events (life-threatening, requiring intervention) will be reported to the IRB within the guidelines set by the IRB.

After 50% of patients enrolled have undergone surgery, evaluation of the rates of post-tonsillectomy bleeding will be carefully evaluated. If any significant increase is noted, the study will be evaluated by the principal investigator for possible discontinuation.

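### The trial is justified by opioid-related respiratory depression, nausea and vomiting, but bleeding is the only safety event pre-specified for comparison by arm

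*Combined protocol and SAP*

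**What the plan says.** **Rationale.** Section 3 reports that "patients with OSA have significantly increased sensitivity to opioids that results in post-operative respiratory" depression and apnea under standard opioid dosing. It adds a "nearly fivefold increase in the odds of developing respiratory complications" for children with OSA compared with those with tonsillitis. Section 5 says of ketorolac that it "does not cause respiratory depression and is not associated with nausea and vomiting", and gives fewer opioid side effects as one reason to study it in OSA.

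**Stated purpose.** Section 4 says: "This study will provide a more comprehensive understanding of the efficacy and safety of the current standard postoperative analgesic regimen", and notes that opioids are prominent in that regimen.

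**Outcomes.** The primary outcome in Section 6 is the amount of opioid needed to bring the FLACC score below 3. For the rest: "The secondary outcomes to be evaluated will be PACU FLACC scores, time required in PACU, incidence of post-tonsillectomy bleeding and total pain medications administered". Section 2 gives matching measures. Section 6 also splits bleeding by whether it needs surgery, and ends data collection at discharge.

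**Analysis.** Section 7 assigns Chi-square tests to binary outcomes and gives bleeding as its one example.

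**Monitoring.** Under Section 19 the principal investigator or a designee takes adverse experiences from the medical record. Subjects are reviewed individually, the principal investigator judges seriousness and relatedness, and serious events are reported to the IRB. Once half the patients have had surgery, "evaluation of the rates of post-tonsillectomy bleeding will be carefully evaluated". No other event is named for that review.

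**The concern.** The planned safety comparison covers one side only. Bleeding is the harm feared from ketorolac, and it is compared. Respiratory depression, nausea and vomiting are the harms attributed to opioids, and no comparison of them is planned.

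If the ketorolac arm needs less morphine, readers will ask whether fewer children had a respiratory event or vomited. Under the present text the answer would rest on an analysis chosen after the data were seen, using events with no agreed definition that were picked up in unstructured chart review. That is weak support for the safety statement in Section 4. An imbalance in respiratory events between arms would also not be tabulated at the half-way review.

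**Working it through.** **1. Rationale against outcomes.** The main check is a comparison of sections.

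| Event | Given as a reason for the trial | Secondary outcome (Sections 2, 6) | Named in analysis (Section 7) | Named for 50% review (Section 19) |
|---|---|---|---|---|
| Respiratory depression, apnea | Yes (3, 5) | No | No | No |
| Nausea, vomiting | Yes (3, 5) | No | No | No |
| Bleeding | Raised as a concern about ketorolac (3, 5) | Yes | Yes | Yes |

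Unplanned intensive care appears in Section 4, but as a source of cost and not as an endpoint. PACU length of stay is an outcome, but at best an indirect marker of opioid harm.

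**2. Is there a figure to reproduce?** No. The total of 120 (Sections 1 and 12) comes without an alpha, power, effect size, event rate or allocation ratio. The documents also give no absolute rate of respiratory events or vomiting; Section 3 gives only relative odds against tonsillitis. The steps below therefore use assumptions: 1:1 allocation, so 120 / 2 = 60 per arm, and a range of event rates.

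**3. Bleeding, for scale.** Section 15 lists bleeding at 3% after tonsil removal and 2% in children with OSA.

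- 60 × 0.02 = 1.2 events per arm
- 60 × 0.03 = 1.8 events per arm

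**4. Precision if a respiratory outcome were added.** With the same rate p in both arms, the half-width of the 95% interval for the risk difference is 1.96 × √(2p(1−p)/60).

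| Assumed p | Expected events per arm | Half-width |
|---|---|---|
| 0.10 | 60 × 0.10 = 6 | 1.96 × √(0.18/60) = 0.107 |
| 0.15 | 60 × 0.15 = 9 | 1.96 × √(0.255/60) = 0.128 |
| 0.20 | 60 × 0.20 = 12 | 1.96 × √(0.32/60) = 0.143 |

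The interval is thus about ±11 to ±14 percentage points at assumed rates of 10-20%. Even so, the expected counts are several times those for bleeding, which the plan already compares.

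**5. Could it serve as a test?** Suppose ketorolac halved the event rate (assumption), with 60 per arm, two-sided alpha 0.05, pooled variance and no continuity correction.

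| Control vs ketorolac rate | Power | Total N for 80% power |
|---|---|---|
| 5% vs 2.5% | 11% | 1812 |
| 10% vs 5% | 18% | 870 |
| 20% vs 10% | 33% | 398 |
| 30% vs 15% | 50% | 242 |
| 40% vs 20% | 67% | 164 |
| 50% vs 25% | 82% | 116 |

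Unless the events are very common, 120 children support an estimate and not a conclusive test.

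**The case against.** **The trial asks about morphine dose, not safety.** The title, primary objective and hypothesis concern opioid sparing, and no section hypothesises fewer respiratory events or less vomiting. A trial may properly measure an intermediate step. This stands: the primary question can be answered as planned. What remains is the gap between the safety statement in Section 4 and the outcomes.

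**The plan does not exclude a comparison.** Section 7 offers bleeding only as an example of a binary outcome, and adverse experiences are collected after enrolment. This also stands. A reader might infer that the trial can yield no randomised evidence on opioid harms; the documents do not support that. They support only that such a comparison is not defined or pre-specified, and that nothing secures uniform ascertainment.

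**Respiratory events are not ignored.** A reader might infer that nobody is watching them. Section 19 provides individual review and IRB reporting of serious events, and Section 14 lets the principal investigator withdraw a child for safety. The gap is narrower: no tabulation by arm.

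**Adding the outcomes would not settle the safety question.** Correct. The half-widths are about as large as the assumed rates at the lower end, and power is low. The case is for pre-specified estimates only.

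**The nausea statements.** Section 5 says ketorolac is not linked to nausea, while Section 15 lists nausea under "1-10% of patients that take Ketorolac may have". It is tempting to treat this as a contradiction that strengthens the point. It does not: Section 5 sets ketorolac against opioids, Section 15 is a list of possible events without a control rate, and all children also receive fentanyl and ondansetron. The wording should be reconciled, but it changes no result and is not part of the case.

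**Conclusion.** The point holds as a gap in pre-specification. The harms used to justify the trial are not among the events it plans to compare, and bleeding is the only safety event pre-specified by arm or named for the half-way review. A comparison of respiratory events and of nausea or vomiting remains possible from collected adverse events, but it would be unplanned and undefined.

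The primary analysis is not affected. What is at stake is the safety statement in Section 4 and how a reduction in morphine could be interpreted. The change is worth making because it is cheap and lets the trial address its own stated purpose. It would deliver estimates with intervals of about ±11 to ±14 points, assuming 60 per arm and event rates of 10-20%; neither assumption comes from the documents.

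**What to change.** 1. **Section 6.** Add two descriptive secondary safety outcomes up to hospital discharge, taken from the record already reviewed under Section 19: (a) any respiratory event, with its components and any desaturation threshold fixed by the investigators before the data are seen; (b) any post-operative nausea or vomiting.
2. **Section 7.** Report both by arm as risk differences with 95% intervals, labelled as estimates and not tests.
3. **Section 19.** At the 50% review, tabulate respiratory events by arm beside bleeding.
4. **Alternative.** If these outcomes are not added, limit the safety statement in Section 4 to opioid dose and the outcomes actually compared.
5. **Minor.** Reconcile the nausea wording in Sections 5 and 15.

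**Cost.** A few extra data fields and one table, with no extra patients, visits or procedures. The respiratory definition needs agreement in advance. Ascertainment will depend on routine charting, since the protocol sets no schedule for recording these events; it helps that PACU nurses are blinded to ketorolac. The intervals will be wide and must be presented that way. The alternative costs only a change of wording.

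### Discretionary end-of-case fentanyl, decided by an anesthesiologist not described as blinded, can bias the PACU morphine comparison; its direction depends on whether fentanyl counts in the outcome

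*Combined protocol and SAP*

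**What the plan says.** Section 6 (Procedures Involved) places two drugs in the same window. The ketorolac group differs by "receiving 0.5mg/kg IV ketorolac at the end of the procedure once hemostasis has been achieved", "while those in the non-ketorolac group will not receive any". A fentanyl dose of 0.5-1 mcg/kg "will be available for administration at the end of the procedure", and "The decision to administer this will be left to the discretion of the attending anesthesiologist for the case". The factors listed for that decision include the patient's condition and "a 20% increase in the heart rate and blood pressure", but the list is open-ended. The order of ketorolac and fentanyl is not given.

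On blinding, Section 6 says: "In PACU, nurses will be blinded to ketorolac administration, but will be informed of all other medications given". No other role is described as blinded and no placebo is mentioned. Section 23 has the pharmacy dispense study drug after randomisation and has it given in the operating room.

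FLACC is scored at 10 minutes, 20 minutes and PACU discharge. A score of 3-5 leads to morphine 0.025 mg/kg and a score of 6-10 to 0.05 mg/kg.

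The outcome has three names. Sections 1, 2 and 4 speak of morphine. Section 6 says both "The total amount of opioid required to obtain a FLACC score of less than 3 will be evaluated as the primary outcome" and "The total amount of morphine required to obtain a FLACC score of less than 3 will be recorded". Section 7 models the amount of narcotic. Nothing says how end-of-case fentanyl is treated in any of these.

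**The concern.** The fentanyl decision comes after allocation and just before the measurements that generate the primary outcome. Randomisation balances the children at baseline, but not a later co-treatment chosen by someone who may know the arm.

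Two sources of imbalance must be kept apart. If a child given ketorolac is more comfortable and so gets no fentanyl, that is part of ketorolac's effect. If a child gets fentanyl because the anesthesiologist knows no ketorolac was given, that is bias. The plan cannot separate them: both drugs are given at the end of the procedure in no stated order, and fentanyl given before ketorolac cannot be a consequence of it.

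The more plausible pattern is extra fentanyl in the non-ketorolac group. With PACU morphine as the outcome, this lowers control-arm morphine and can conceal real opioid sparing. What is at stake is the trial's main answer, and the problem would occur even if the protocol were followed exactly.

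**Working it through.** **No stated figure to reproduce.** Section 12 gives 120 participants. The documents give no alpha, power, effect, SD, allocation ratio, fentanyl rate or displacement. What follows is an illustration.

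**Inputs from the documents.** 120 children; three FLACC scores; morphine steps of 0, 0.025 and 0.05 mg/kg; the amount needed to bring FLACC below 3.

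**Assumptions.** 60 per arm; two-sided 5% t-test; 80% power before any bias; each score falls in the three bands with equal chance, independently; counting stops at the first score below 3; fentanyl is unrelated to need; each fentanyl dose displaces up to 0.025 or 0.05 mg/kg of morphine, but never more than the child would have received.

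**Step 1: distribution of PACU morphine, M.** The 27 equally likely score sequences give:

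| M (mg/kg) | 0 | 0.025 | 0.05 | 0.075 | 0.10 | 0.125 | 0.15 |
|---|---|---|---|---|---|---|---|
| Sequences | 9 | 3 | 4 | 3 | 4 | 3 | 1 |

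The mean is 0.0528 and the mean square 0.005116, so SD = √(0.005116 − 0.0528²) = 0.048 mg/kg.

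**Step 2: effect with 80% power.** The noncentral t with 118 df needs a standardised difference of 0.5157. The effect is 0.5157 × 0.0483 = 0.0249 mg/kg.

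**Step 3: mean displacement per fentanyl dose, m = E[min(dose, M)].**
- Up to 0.025: 0.025 × 18/27 = 0.0167 mg/kg.
- Up to 0.05: 0.025 × 3/27 + 0.05 × 15/27 = 0.0306 mg/kg.

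**Step 4: PACU morphine only.** Hidden effect = (qC − qK) × m, where qC and qK are the proportions given arm-driven fentanyl in the control and ketorolac groups. Power uses noncentrality (0.5157 − hidden/SD) × √30.

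| Control excess | Displaces up to | Hidden (mg/kg) | Share of effect | Power |
|---|---|---|---|---|
| 20 points | 0.025 | 0.0033 | 13% | 68% |
| 20 points | 0.05 | 0.0061 | 25% | 56% |
| 10 points | 0.025 | 0.0017 | 7% | 74% |
| 10 points | 0.05 | 0.0031 | 12% | 69% |
| 5 points | 0.025 | 0.0008 | 3% | 77% |
| 5 points | 0.05 | 0.0015 | 6% | 75% |

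If fentanyl goes to children with greater need, the cap matters less. With no cap, 20 points would hide 0.2 × 0.025 / 0.0249 = 20% or 0.2 × 0.05 / 0.0249 = 40%. An excess in the ketorolac group would inflate the effect by the same amounts as in the table.

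**Step 5: fentanyl counted.** If each dose enters the outcome as f mg/kg of morphine equivalent, the observed saving changes by (qC − qK) × (f − m). It shrinks if f < m, is unchanged if f = m, and grows if f > m. For a 20-point control excess and m = 0.0167, an assumed f of 0.05 adds 0.2 × (0.05 − 0.0167) = 0.0067 mg/kg, an overstatement of 27%. The same prescribing pattern can therefore hide or exaggerate the effect, depending on a definition the plan leaves open.

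**The case against.** The plan has real protections. The nurses who score FLACC are blinded to ketorolac, and the morphine steps are fixed by the score. The heart-rate and blood-pressure cue is objective and applies to both arms. Total pain medication during hospitalisation is already a secondary outcome and plausibly captures this fentanyl. Every imbalance used above is assumed, and the truly arm-driven part could be close to zero.

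The point about size stands: the figures show what could happen and do not estimate what will. The protections do not dispose of the mechanism. Blinded scoring comes after the fentanyl decision. The cue is one factor among several in a discretionary choice. A secondary outcome may reveal an imbalance but leaves the primary comparison as it is. The adjustment in Section 7 is for patient and surgical characteristics, which does not cover this drug.

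Three stronger readings are tempting and should be resisted.
- A reader might infer that the protocol says the anesthesiologist is unblinded. It does not; this follows from blinding that names only the nurses, the absence of a described placebo, and dosing in the operating room.
- A reader might treat any fentanyl imbalance as bias. Lower use because ketorolac works is not bias.
- A reader might let morphine accrue at all three scores regardless of earlier ones. Under otherwise similar assumptions that gives power as low as 54% or 29% and up to half the effect hidden. It does not fit an outcome defined as the amount needed to bring FLACC below 3.

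**Conclusion.** The concern holds and should be fixed, with medium confidence. Discretionary fentanyl, decided by someone who by inference knows the arm, can bias the primary comparison, and the plan neither prevents this nor says how that fentanyl is handled.

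The direction is conditional. If the outcome is PACU morphine only, the most natural reading of Sections 1, 2 and 4, extra fentanyl in controls hides a ketorolac effect. A false effect would need an excess in the ketorolac group, which is possible but less expected. If fentanyl is counted under the 'opioid' or 'narcotic' wording, the bias can shrink, cancel or reverse with the conversion ratio.

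The size cannot be known from the documents. Under the stated assumptions it is modest at a 5-point imbalance and material at 20 points. The case for acting rests on the mechanism and the low cost of prevention, not on any one of these figures.

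**What to change.** 1. **Mask the decision (Sections 6 and 23).** Have the pharmacy, which already dispenses study drug after randomisation, supply a matching masked saline syringe for the non-ketorolac group, and add an emergency code-break procedure. The fentanyl decision is then made blind, whichever drug is given first.
2. **Define one primary outcome (Sections 1, 2, 4, 6 and 7).** Reconcile 'morphine', 'opioid' and 'narcotic', and state whether end-of-case fentanyl counts.
3. **Report and support (Section 7).** Report end-of-case fentanyl by arm: use, dose, and whether before or after study drug. Prespecify total opioid from end of procedure to PACU discharge as a supporting analysis, with the conversion ratio varied.

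No dose or rescue criterion changes.

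**Cost.** An amendment, pharmacy preparation of about 60 saline syringes if allocation is 1:1 (the ratio is not stated), and a code-break procedure that the documents do not now contain. Operating-room staff would not know ketorolac status in a trial that monitors bleeding; the code break has to cover that. Items 2 and 3 are wording plus fentanyl dose and time, which should be in the anesthesia record, and need no new visit. The supporting result depends on the conversion ratio. If masking is not adopted, it also carries arm-aware prescribing and should be read with caution.
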